## 6.2 Motion management

Motion management must be employed for moving targets. Breath hold treatment, which is strongly preferred, may be either in inspiration or expiration at the discretion of the treating physician, based on patient tolerance, reproducibility, and proximity of the target to OARs. Patients who will be treated in breath hold should be able to reproducibly hold their breath such that a high quality 17-25 second volumetric MRI scan can be obtained with minimal motion artifact.

Patients may be treated using free breathing gating and it is strongly recommended that an MRI-compatible abdominal compression device be used to limit diaphragmatic excursion and tumor motion.

## 6.3 Daily MR image-guidance

The use of image-guidance using MRI is mandatory. This will include a pre-treatment volumetric MRI using a TRUFI sequence that will be obtained prior to each delivered fraction. Alignment should be to soft tissue including the target lesion.

## 6.4 Target Volumes

### 6.4.1. Gross Tumor Volume (GTV)

This will include visible tumor as seen on MRI/CT.

### 6.4.2 Clinical Target Volume (CTV)

The use of a CTV is optional and at the discretion of the treating physician.

It is suggested that the CTV should be an expansion of 2-5 mm from the GTV, edited out of anatomic barriers to microscopic tumor spread.

### 6.4.3 Planning Target Volume (PTV)

It is preferred that a 3 mm uniform expansion from the GTV/CTV define the PTV. However, a 5 mm uniform expansion will also be permitted.

## 6.5 Prescription dose and fractionation

Each lesion will be treated in one fraction.

The prescription dose is dependent on the anatomic location of the lesion and based on previously published safety data.

- Lung (30-34 Gy. BED10 = 120-149.6 Gy)
- Liver (35-40 Gy; BED10 = 157.5-200 Gy)
- Pancreas (25 Gy; BED10 = 93.6 Gy)
- Kidney (25 Gy; BED10 = 93.6 Gy)
- Adrenal gland (25 Gy; BED10 = 93.6 Gy)
- Abdominal/pelvic lymph node (25 Gy; BED10 = 93.6 Gy)

If a CTV is used, then it will be prescribed the same dose as the GTV.

## 6.6 Organs at risk and constraints

THORACIC			
Structure	Contouring	Constraint	
Spinal cord	Spinal canal extending $\geq$ 2 cm cranial and caudal to the PTV	$\leq$ 0.03 cc $\leq$ 0.35 cc $\leq$ 1.2 cc	14 Gy 10 Gy 7 Gy
Skin	Outer 5 mm of the body surface extending $\geq$ 2 cm cranial and caudal to the PTV	$\leq$ 0.03 cc $\leq$ 10 cc	26 Gy 23 Gy
Lungs (right and left)	Combined right and left lungs minus GTV	$\leq$ 1500 cc $\leq$ 1000 cc	7 Gy 7.4 Gy
Proximal trachea	Trachea extending $\geq$ 2 cm cranial to the PTV or $\geq$ 5 cm cranial to the carina (whichever is most cranial) extending caudally to the cranial aspect of the proximal bronchial tree	$\leq$ 0.03 cc 4 cc	20.2 Gy 10.5 Gy
Proximal bronchial tree	Distal 2 cm of the trachea, carina, right/left main stem bronchi, right/left upper lobe bronchi, intermedius bronchus, right middle lobe bronchus, lingular bronchus, right/left lower lobe bronchi; lobar bronchi contour will not extend into the segmental bifurcation	$\leq$ 0.03 cc 4 cc	20.2 Gy 10.5 Gy

Heart	Superiorly at the level of the bifurcation of the pulmonary artery inferiorly to the apex of the heart, including the pericardium	$\leq 15$ cc $\leq 0.03$ cc	16 Gy 22 Gy
Great vessels	Aorta and vena cava (not the pulmonary artery/vein) extending $\geq 2$ cm cranial and caudal to the PTV	$\leq 10$ cc $\leq 0.03$ cc	31 Gy 37 Gy
Chest wall	2 cm radial expansion of the ipsilateral lung excluding mediastinal soft tissue, anterior vertebral body, and any extension outside of the external body contour; extended 2 cm cranial and caudal of the PTV	$\leq 0.03$ cc $\leq 5$ cc $\leq 1$ cc	30 Gy 27 Gy 22 Gy
Ribs	Bone and marrow of the ribs as seen on bone windows within 5 cm of the PTV to not include the intercostal spaces	$\leq 0.03$ cc $\leq 1$ cc	30 Gy 22 Gy
Brachial plexus	Subclavian and axillary vessels starting proximally at the bifurcation of the brachiocephalic trunk into the jugular/subclavian veins (or carotid/subclavian arteries) and following along the route of the subclavian vein to the axillary vein ending after the neurovascular structures cross the second rib	$\leq 0.03$ cc $\leq 3$ cc	17.5 Gy 14 Gy
Esophagus	All muscular layers extending $\geq 2$ cm cranial and caudal to the PTV	$\leq 0.03$ cc $\leq 10$ cc	12.4 Gy 11.2 Gy
Stomach	From the gastroesophageal junction to the pylorus	$\leq 0.03$ cc $\leq 10$ cc	12.4 Gy 11.2 Gy

ABDOMEN/PELVIS			
Structure	Contour	Volume	Dose
Liver - GTV	Entire liver minus GTV	$\leq 700$ cc	9.1 Gy
Spinal cord	Spinal canal extended $\geq 2$ cm cranial and caudal to the PTV	$\leq 0.03$ cc $\leq 0.35$ cc $\leq 1.2$ cc	14 Gy 10 Gy 7 Gy
Skin	Outer 5 mm of the body surface extending $\geq 2$ cm cranial and caudal to the PTV	$\leq 0.03$ cc $\leq 10$ cc	26 Gy 23 Gy

Chest wall	2 cm radial expansion of the ipsilateral lung excluding mediastinal soft tissue, anterior vertebral body, and any extension outside of the external body contour; extended 2 cm cranial and caudal of the PTV.	$\leq 0.03$ cc $\leq 5$ cc $\leq 1$ cc	30 Gy 27 Gy 22 Gy
Esophagus	All muscular layers extending $\geq 2$ cm cranial and caudal to the PTV	$\leq 0.03$ cc $\leq 10$ cc	12.4 Gy 11.2 Gy
Stomach	From the gastroesophageal junction to the pylorus	$\leq 0.03$ cc $\leq 5$ cc $\leq 10$ cc	12.4 Gy 11.2 Gy 9 Gy
Duodenum	From the pylorus to 4 th part of duodenum	$\leq 0.03$ cc $\leq 5$ cc $\leq 10$ cc	12.4 Gy 11.2 Gy 9 Gy
Small bowel	Small bowel loops from the jejunum to 2 cm caudal to PTV	$\leq 0.03$ cc $\leq 5$ cc $\leq 10$ cc	12.4 Gy 11.2 Gy 9 Gy
Large bowel	Large bowel loops $\geq 2$ cm cranial and caudal to the PTV	$\leq 0.03$ cc $\leq 5$ cc $\leq 10$ cc	18.4 Gy 11.2 Gy 9 Gy
Kidney (right and left)	Entire right and left kidneys	Mean V10	7 Gy 33%
Rectum	From the rectosigmoid junction to anal canal	$\leq 0.03$ cc $\leq 5$ cc $\leq 10$ cc	18.4 Gy 11.2 Gy 9 Gy
Bladder	Entire bladder	$\leq 15$ cc	11.4 Gy

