## 6.7 Treatment planning

Step-and-shoot intensity modulated radiation therapy (IMRT) using 6 MV FFF photons will be used. Ideally,  $\geq 95\%$  of the PTV and  $\geq 99\%$  of the GTV/CTV should receive  $\geq 100\%$  of the prescribed dose. However, depending on the proximity of the normal organs, especially gastrointestinal (GI) luminal structures, that may not be achievable without violating normal organ constraints. If the proximity of OARs results in a clinically significant reduction in dose to the GTV on the original plan, defined as  $\leq 80\%$  receiving  $\geq 100\%$  of the prescribed dose and/or  $\leq 90\%$  receiving  $\geq 90\%$  of the prescribed dose, then multi-fraction SBRT off study should be considered although will not be required. If patients remain on study in this scenario, then attempts should be made to optimize the internal anatomy on the day of treatment to improve target dose coverage as much as reasonably possible, for example ensuring appropriate bladder, rectal, or stomach filling.

Hotspots of at least 120-130% of the prescription dose are permitted, and in fact are encouraged, if they are located within the GTV and not in organs at risk (OARs).

Meeting all OAR constraints should be prioritized, even at the expense of target volume coverage, while secondarily optimizing target volume coverage.

For patients treated to multiple lesions, separate plans will be generated for each lesion. A planning CT dataset that includes all targets and relevant critical structures in the imaging study should be obtained when possible. The cumulative dose to OARs from all treatment plans should be assessed. If multiple lesions are treated, then OAR dose constraints as described in section 6.6 should be considered to be cumulative constraints that should be met in total across all treatment plans regardless of the number of lesions treated.

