## 6.8 Treatment delivery and on-table adaptive replanning

All patients will receive radiation therapy using photons on the MRIdian Linac system for alignment, dose prediction, tracking, gating, and on-table adaptive planning when clinically indicated.

For each delivered fraction, a volumetric MRI data set will be obtained using system integrated sequences; the preferred sequence is a balanced gradient echo most similar to Siemens True FISP scan with T2\*/T1 weighted image-characteristics with at least a 1.5 x 1.5 x 3.0 mm image matrix resolution. The external contour of the patient should be inside the field of view where there are beam angles that will be used for treatment.

The target volume will be rigidly aligned to a reference position by virtual couch movement in cranio-caudal, left-right and anterior-posterior direction to optimally align with the planned treatment isocenter. Depending on operator assessment, these shifts are then executed, and treatment is initiated.

If optimal target to isocenter alignment cannot be achieved, system integrated deformable image registration between the primary treatment image data (used for simulation and treatment planning) and the respective fraction MRI dataset will be performed. Original plan contours are propagated onto the respective fraction MRI dataset. If on-table adaptive planning is clinically indicated, then all tumor volumes and

critical structures within 3 cm radially and 2 cm cranial-caudal from the surface of the PTV will be re-contoured as needed on the volumetric high-quality MRI data set.

An estimated delivered dose will be calculated and saved using the software on the console (dose prediction). An adapted radiation therapy plan is created based on physician assessment of medical necessity. General guidelines to establish medical necessity include but are not limited to the following:

- Any OAR constraint is violated. The same constraints used to develop the original plan will be used to on the day of treatment to determine the need to create an adapted plan.
- Reduction in GTV and/or PTV covered by the prescription isodose compared to the original plan.
- Favorable shift in the relation between GTV and dose-limiting OARs, such that adaptive planning would likely improve the coverage of the GTV.

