For patients treated to multiple lesions, adaptive replanning may be required in order to ensure that cumulative dose to OARs meets constraints. As the original treatment plans are required to cumulatively meet all OAR constraints, adaptive replanning must be performed on the day of treatment delivery in order to achieve at least the same dose avoidance as the original plans.

Adaptive dose re-planning does not need to be performed if the dose prediction shows compliance with minimum dose coverage of the GTV and adherence to upper dose/volume limits of all OARs.

If multiple lesions are to be treated on this study, it is recommended that each one should be treated separately as treatment of multiple lesions may significantly prolong total treatment time, which may be poorly tolerated by the patient. However, treatment of multiple lesions on this trial during the same session is permitted if the treating physician believes that treatment would be completed within a feasible amount of time.

During radiation dose delivery, continuous cine MR image acquisition in at least one principal plane (suggested sagittal, but at the discretion of the treating physician) is mandatory for soft tissue tracking and radiation beam gating. To this end, a tracking slice of 7-10 mm thickness will be positioned to include a cross-sectional cut of the target for intra-fractional soft tissue tracking. The tracking/gating volume will be preferably delineated based on the GTV, or otherwise on a well visualized surrogate in proximity to the GTV.

The software should be set so that if 5% or more of the tracked target extends outside of the boundary the beam will gate off. For soft tissue tracking and gating, a minimum cine frame rate of 4 frames/second is mandatory throughout dose delivery although higher frame rates (e.g., 8 frames/second) may be used if available.

During study treatment, a time log will be used to record the following events, at a minimum:

- Patient enters the treatment room
- Volumetric scan initiated
- Target volume/OAR contouring started
- Target volume/OAR contouring ended
- Predicted dose calculation completed
- Treatment plan re-optimization finalized (if performed)
- Treatment delivery started
- Treatment delivery completed

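### Section 6.6 limits liver and lung dose only by fixed-cc caps, so the volume a compliant plan is bound to spare shrinks with the organ; a minimum spared volume beside the caps would close this

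*Combined protocol and SAP*

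**What the plan says.** The Lungs row of section 6.6 applies to both lungs combined, less the GTV. Its volume limits are "\leq$ 1500 cc $\leq$ 1000 cc", set against 7 Gy and 7.4 Gy. The liver row applies to the liver less the GTV and has one line, at most 700 cc at 9.1 Gy. Both rows use the same form as the other maximum-volume rows, such as spinal cord at most 0.03 cc at 14 Gy. The row for "Entire right and left kidneys" is different: it sets a mean of 7 Gy and a V10 of 33%, both of which scale with organ size.

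Section 6.7 gives these limits first rank: "Meeting all OAR constraints should be prioritized, even at the expense of target volume coverage". For multiple lesions they are "cumulative constraints that should be met in total across all treatment plans regardless of the number of lesions treated". When OAR proximity cuts GTV dose substantially, "multi-fraction SBRT off study should be considered although will not be required".

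Section 6.8 carries the limits to the treatment day. One listed ground for adapting is "Any OAR constraint is violated. The same constraints used to develop the original plan will be used to on the day of treatment". Adaptation is not needed when GTV coverage is adequate and there is "adherence to upper dose/volume limits of all OARs". For multiple lesions, adaptation is required "in order to achieve at least the same dose avoidance as the original plans".

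Sections 5.1 and 5.2 allow 1 to 10 lesions of up to 5 cm and set no liver or lung volume threshold. Section 6.5 prescribes 35-40 Gy to liver and 30-34 Gy to lung in one fraction.

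**The concern.** A cap on irradiated volume protects what is left over. In a large organ the remainder is large. In a small or previously resected organ the same cap can permit most or all of the uninvolved tissue to reach the dose, and the plan still complies. The patient with the least reserve gets the weakest written protection.

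The later safeguards refer back to the same caps. A predicted dose within the cap is not an OAR violation under section 6.8. The multi-lesion rule compares with original plans that themselves need only meet the caps. The off-study option in section 6.7 responds to lost target coverage, which a loose cap does not cause. At stake is normal-tissue injury after a single large fraction, with doses summed over as many as ten lesions.

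**Working it through.** The plan states no spared volume or organ size, so there is no figure of its own to reproduce here.

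**Inputs from section 6.6.** Liver cap 700 cc (9.1 Gy); lung caps 1500 cc (7 Gy) and 1000 cc (7.4 Gy).

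**Assumed inputs.** V, the organ volume less the GTV, is shown over a range. F, a minimum spared volume, uses placeholders of 700 cc (liver) and 1500 cc (lung) that reuse the printed figures.

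**Formulas.**
- Cap alone: permitted at dose = min(cap, V); guaranteed below dose = max(0, V - cap).
- Cap plus floor, for V at least F: permitted = min(cap, V - F); guaranteed = max(V - cap, F).
- The floor is the tighter rule when V < cap + F.

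| Structure, dose | V (cc) | Cap permits (share of V) | Guaranteed below dose | Permitted with floor |
|---|---|---|---|---|
| Liver, 9.1 Gy | 1500 | 700 (47%) | 800 | 700 |
| | 1200 | 700 (58%) | 500 | 500 |
| | 1000 | 700 (70%) | 300 | 300 |
| | 800 | 700 (88%) | 100 | 100 |
| | 700 | 700 (100%) | 0 | 0 |
| Lungs, 7 Gy | 3000 | 1500 (50%) | 1500 | 1500 |
| | 2500 | 1500 (60%) | 1000 | 1000 |
| | 2000 | 1500 (75%) | 500 | 500 |
| | 1500 | 1500 (100%) | 0 | 0 |

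At 7.4 Gy the lung guarantee is V - 1000: 1500, 1000, 500 and 0 cc at V = 2500, 2000, 1500 and 1000 cc.

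**Example.** For a 1000 cc liver, any predicted volume from just over 300 cc up to 700 cc at 9.1 Gy passes today. With the placeholder floor it would be a violation and an OAR ground for adapting.

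**Where the floor acts.** Liver: V < 700 + 700 = 1400 cc. Lungs: V < 1500 + 1500 = 3000 cc. Other floor values move this point: liver floors of 500 or 1000 cc act below 1200 or 1700 cc, and lung floors of 1000 or 2000 cc act below 2500 or 3500 cc. No second lung floor is needed, because tissue below 7 Gy is also below 7.4 Gy.

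**Can the cap be approached?** Treat a 5 cm GTV as a sphere of 65 cc. The liver cap is used up when the 9.1 Gy surface encloses 700 + 65 = 765 cc, a radius of 5.67 cm. With a 5 mm margin the PTV radius is 3.0 cm, so that surface lies about 2.7 cm outside the PTV. The dose there is 9.1/40 = 23% to 9.1/35 = 26% of prescription. This assumes that the whole sphere lies inside the liver. In an 800 cc liver it would fill 765/(800 + 65) = 88% of liver plus GTV, so the sketch does not show that the cap is reached in the smallest organs.

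**The case against.** The strongest reply is that the bounds are formal and no plan is shown to reach them. That stands in part. Every V is assumed. Limits on neighbouring organs also restrain dose spread: at most 10 cc at 9 Gy for stomach, duodenum and bowel, mean 7 Gy for kidney, and at most 1.2 cc at 7 Gy for cord. The lung caps act together, so irradiating all of a 1500 cc lung to 7 Gy would need at least 500 cc lying between 7 and 7.4 Gy. These facts make the extremes less likely, but none sets a minimum spared volume.

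A second reply is that clinicians are not bound to the caps. This also stands. The adaptation grounds in section 6.8 are an open list under physician assessment of medical necessity, so a physician may adapt to spare a small liver with no cap exceeded. Exclusion 6 allows judgement on patient safety, and under section 11.4 the DSMC can recommend dose adjustment or dropping a treatment site. A reader might infer that the plan prevents adaptation in small organs; it does not. These are judgements, however, and the DSMC's scheduled toxicity review and the closure rule in section 11.5 act after treatment.

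A third reply is that 700 and 1500 cc have no source as floors. Correct: they are placeholders. A cc floor for lung also depends on the breathing phase, which section 6.2 leaves open. A floor is itself a fixed volume, but it fixes the amount spared, whereas the cap lets that amount fall with V.

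A reader might also infer that the inequality sign is a misprint and that spared volumes were meant. The documents do not show this. The lung lines are more coherent as caps: if at least 1500 cc had to stay below 7 Gy, a demand for 1000 cc below 7.4 Gy would add nothing.

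**Conclusion.** The point holds as a minor gap in the written dose limits. For liver and lung, a compliant plan guarantees only max(0, V - cap), which falls one cc for each cc of organ lost and reaches zero at 700 cc of liver (9.1 Gy) and 1500 cc of lung (7 Gy). No other dose limit, eligibility criterion or mandatory adaptation rule replaces it.

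The result rests on reading the rows as printed and on plans that meet the limits, which section 6.7 words as a recommendation. The values are guaranteed minimums, not predictions. With no organ volumes in the documents, the number of patients affected cannot be stated and may be small. Nothing here shows that the caps are unsafe in general, and patients with large organs are unaffected. The sample size and the operating characteristics in section 13.4 do not depend on the point.

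**What to change.** Keep the caps and add two lines to section 6.6: a minimum volume of liver minus GTV that stays below 9.1 Gy, and a minimum volume of lungs minus GTV that stays below 7 Gy. The sponsor should set and justify both values (700 and 1500 cc are placeholders only) and confirm whether the printed rows were meant as spared volumes. If they were, restate the rows instead.

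Assess the floor on the planning scan in the treatment breathing phase, cumulatively over all plans. Recheck it on the day with the propagated whole-organ contour, because section 6.8 asks for re-contouring only within 3 cm radially and 2 cm cranio-caudally of the PTV. State that a patient whose uninvolved organ is smaller than the floor is treated off study, since no replan can meet it; the existing off-study wording in section 6.7 is optional and does not settle that case.

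The cost is two table lines and one volume check per relevant plan. With the placeholder values the check acts only for liver minus GTV under 1400 cc or lungs minus GTV under 3000 cc. Some of those patients may lose target coverage, need extra adaptation time that counts towards the 90-minute feasibility criterion, or be treated off study. Endpoint definitions, visits and sample size stay as they are.

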## 6.7 Treatment planning

Step-and-shoot intensity modulated radiation therapy (IMRT) using 6 MV FFF photons will be used. Ideally,  $\geq 95\%$  of the PTV and  $\geq 99\%$  of the GTV/CTV should receive  $\geq 100\%$  of the prescribed dose. However, depending on the proximity of the normal organs, especially gastrointestinal (GI) luminal structures, that may not be achievable without violating normal organ constraints. If the proximity of OARs results in a clinically significant reduction in dose to the GTV on the original plan, defined as  $\leq 80\%$  receiving  $\geq 100\%$  of the prescribed dose and/or  $\leq 90\%$  receiving  $\geq 90\%$  of the prescribed dose, then multi-fraction SBRT off study should be considered although will not be required. If patients remain on study in this scenario, then attempts should be made to optimize the internal anatomy on the day of treatment to improve target dose coverage as much as reasonably possible, for example ensuring appropriate bladder, rectal, or stomach filling.

Hotspots of at least 120-130% of the prescription dose are permitted, and in fact are encouraged, if they are located within the GTV and not in organs at risk (OARs).

Meeting all OAR constraints should be prioritized, even at the expense of target volume coverage, while secondarily optimizing target volume coverage.

For patients treated to multiple lesions, separate plans will be generated for each lesion. A planning CT dataset that includes all targets and relevant critical structures in the imaging study should be obtained when possible. The cumulative dose to OARs from all treatment plans should be assessed. If multiple lesions are treated, then OAR dose constraints as described in section 6.6 should be considered to be cumulative constraints that should be met in total across all treatment plans regardless of the number of lesions treated.

For targets in the abdomen and pelvis, a PRVGI should be created that is defined as the union of the stomach + duodenum + small bowel + large bowel contours with a 5 mm uniform expansion. If there is any overlap of the PRVGI with the PTV then a PTVopt should be created, which is the PTV minus any overlap of the PRVGI. The treatment plan should be prescribed to the PTVopt instead of the PTV, ensuring that all OAR constraints are met. The dose to the overlapped region of the PTV and PRVGI should be as high as possible while meeting all OAR constraints, although no minimum coverage will be required. If there is not overlap of the PRVGI with the PTV then the treatment plan should be prescribed to the PTV.

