## 13. STATISTICAL METHODS

### 13.1 Evaluation of study objectives

#### 13.2 Primary objectives

The point estimate for feasibility will be reported as a binary variable with its 95% confidence interval. Feasibility will be achieved if all are true:

- Successful completion of treatment to each lesion within 3 working days of intended treatment completion
- Successful completion of treatment to each lesion within 90 minutes from the patient entering the treatment room until treatment completion. Any machine downtime during treatment delivery should be recorded and will not be included when assessing the time for completion of treatment.
- Image guidance verification of treatment delivery within 5 mm of the planned delivery

The point estimate for tolerability will be reported as a binary variable with its 95% confidence interval. Tolerability will be achieved if all are true:

- No greater than 4 of 30 patients experience grade 3 or higher acute toxicity within 90 days of completing SABR
- No grade 5 toxicity is attributed to SABR

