### 13.4 Sample size determination

For this study, a sample size 30 is assessed pragmatically and not based on hypothesis testing. Table 1 shows 90% and 95% confidence intervals for different feasibility rates.

Sample size	Feasible cases	Feasibility rate	90% CI	95% CI
30	27	90%	76% - 97%	73% - 98%
30	24	80%	64% - 91%	61% - 91%
30	21	70%	53% - 83%	51% - 85%

Following criteria will be implemented for this feasibility study to advance to a phase II/III trial:

1. Grade  $\geq 3$  toxicity in no greater than 4 out of 30 patients
2. No grade 5 toxicity
3. Treatment feasibility rate of at least 80%

With a sample size of 30, if the true underlying grade 3 toxicity rate is 10.5%, the probability of no greater than 15% of patients in the sample (maximum 4 out of 30) suffering a grade 3 or higher acute toxicity is 80%. In other words, if the true underlying grade 3 toxicity rate is 10.5%, the probability of satisfying the specified tolerability threshold for escalation to a phase II/III trial is 80%. If the true underlying grade 3 toxicity rate is 21.4%, the probability of no greater than 15% of patients (maximum 4 out of 30) should suffer a grade 3 or higher acute toxicity is 20%. In other words, if the true underlying grade 3 toxicity rate is 21.4%, the probability of satisfying the specified tolerability threshold for escalation to a phase II/III trial is 20%.

With a sample size of 30, if the true underlying feasibility rate is 83.9%, the probability of at least 24 out of 30 patients satisfying the feasibility criteria is 80%. In other words, if the true underlying feasibility rate is 83.9%, the probability of satisfying the specified feasibility threshold for escalation to a phase II/III trial is 80%. If the true underlying feasibility rate is 71.3%, the probability of at least 24 out of 30 patients satisfying the feasibility criteria is 20%. In other words, if the true underlying feasibility rate is 71.3%, the probability of satisfying the feasibility tolerability threshold for escalation to a phase II/III trial is 20%.

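### No rule scores patients whose anatomy prevents adequate single-fraction coverage, so they need not count against the feasibility rate

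*Combined protocol and SAP*

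**What the plan says.** Section 13.2, like section 2.2 and the Protocol Summary, makes feasibility depend on three items:

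- "Successful completion of treatment to each lesion within 3 working days of intended treatment completion"
- a time limit of 90 minutes for each lesion, measured from entry to the room to the end of treatment (section 13.2 leaves machine downtime out of this time)
- "Image guidance verification of treatment delivery within 5 mm of the planned delivery"

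None of them refers to target dose or coverage. The term successful completion is not defined, and no section names the feasibility denominator.

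Section 6.7 recognises that nearby organs may prevent full coverage. It calls the loss of GTV dose clinically significant when, on the original plan, at most 80% of the GTV gets the full prescribed dose and/or at most 90% gets at least 90% of it. In that case, "then multi-fraction SBRT off study should be considered although will not be required". A patient who stays on study is treated with best efforts to improve coverage on the day. The order of priority is explicit: "Meeting all OAR constraints should be prioritized, even at the expense of target volume coverage". Where the PTV overlaps the gastrointestinal planning-risk volume, there is no coverage floor.

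Under section 7.2 a patient is enrolled on consent and confirmed eligibility. The screening list in section 8.1 contains no simulation or planning step. Section 12.2 allows replacement of a patient who leaves before the first efficacy scan for a reason other than toxicity or progression, and requires such cases to be recorded and reported.

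In section 13.4, one of the three criteria for moving to phase II/III is "Treatment feasibility rate of at least 80" percent.

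**The concern.** The objective is to learn whether SABR can be delivered feasibly in one fraction. Anatomy that rules out adequate coverage is an obvious way for that to fail, and the protocol foresees it. Neither route that section 6.7 offers has a scoring rule:

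- **Off study.** The patient is already enrolled when planning reveals the problem. Replacement is permitted, because the reason is neither toxicity nor progression. With no denominator defined, the analysis can be run on 30 treated patients and this failure drops out of the rate.
- **On study.** The patient can be treated with the coverage loss that section 6.7 calls clinically significant and still be a full success if the day, minute and millimetre items are met.

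At stake is the decision to advance. The feasibility rate could reach 80% partly because such patients were left out, or were counted the same as patients with full coverage.

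**Working it through.** **1. Reproducing the plan's figures.** With n = 30 and a pass at 24 or more, the chance of passing at a true rate p is P(X ≥ 24) = Σ C(30,k) p^k (1−p)^(30−k), summed over k = 24 to 30.

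- p = 0.839 gives 0.802 (section 13.4 states 80%).
- p = 0.713 gives 0.200 (section 13.4 states 20%).

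Both stated figures are correct. The question is what the endpoint counts.

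**2. Off-study route.** Let x be the successes among 30 analysed patients and r the number replaced because coverage was inadequate. The rate over all enrolled patients is x/(30 + r).

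- x = 24, r = 0: 24/30 = 80.0%, passes.
- x = 24, r = 1: 24/31 = 77.4%, does not pass.
- x = 27, r = 3: 27/33 = 81.8%, passes.
- x = 27, r = 4: 27/34 = 79.4%, does not pass.

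At the boundary one replaced patient changes the decision. At 27/30 it takes four.

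**3. On-study route.** Let s be the true rate of meeting the three written items. Let c be the share of those successes whose delivered plan shows the section 6.7 coverage loss. The rate on a stricter definition is s(1 − c). The documents give no value for c, so 5% to 20% is an assumption. It is taken to be the same for all patients, with patients independent.

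| c | s(1 − c), s = 83.9% | P(at least 24/30) | s(1 − c), s = 90% | P(at least 24/30) |
|---|---|---|---|---|
| 0 (as written) | 83.9% | 80% | 90.0% | 97% |
| 5% | 79.7% | 59% | 85.5% | 87% |
| 10% | 75.5% | 37% | 81.0% | 66% |
| 15% | 71.3% | 20% | 76.5% | 42% |
| 20% | 67.1% | 9% | 72.0% | 22% |

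At s = 83.9%, a share of 15% gives 0.839 × 0.85 = 0.713. That is the rate at which section 13.4 itself puts the chance of passing at 20%.

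In counts: 26/30 = 86.7% meets the criterion as written. If 4 of the 26 had the coverage loss, the stricter rate would be 22/30 = 73.3%, which does not.

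Holding the bar at 24/30 while tightening the definition can only lower the chance of passing. The table therefore shows how much the definition matters, not an error in section 13.4.

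**The case against.** The best defence is that the endpoint measures what the hypothesis in section 2.1 asks: tolerability and completion in a practical time. Local control is assessed separately, and a strategy that openly ranks organ limits above coverage may fairly be judged as it is. Making coverage a required element of the endpoint is a debatable choice. This part stands, and it is why the stricter rate is proposed beside the primary one.

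A reader might infer that such anatomy never counts as infeasible. The documents do not go that far. Replacement is optional and must be reported. If all enrolled patients are counted, one who was never treated plainly fails the first item. Difficult anatomy can also fail the 90-minute item, for example through re-contouring and adaptive replanning under section 6.8. What remains is that nothing requires the failure to be counted.

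A reader might also infer that these patients are failures by the protocol's own threshold. That threshold applies to the original plan and prompts consideration of another treatment; it does not define failed single-fraction delivery. Sections 6.7 and 6.8 provide for better coverage on the day, so the delivered plan may be adequate. Section 6.8 does mention minimum GTV coverage when deciding whether to adapt, but gives no number and no link to feasibility.

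Finally, giving up dose to protect organs might also make tolerability easier to meet. That is plausible, but nothing in the documents shows that both primary results are biased in the same direction.

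**Conclusion.** The point holds in this form: anatomy that prevents adequate single-fraction coverage need not count against feasibility, because no rule scores it.

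The off-study gap follows from the text of sections 6.7, 7.2, 12.2 and 13.2 taken together. It can reverse the decision to advance with a single patient at the boundary (80.0% against 77.4%), and matters less when the observed rate is well above 80%.

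The on-study gap is equally clear in the text, but its size is unknown. The fall from 80% to between 59% and 9% at a true rate of 83.9% rests on an assumed share of 5% to 20% and on applying the section 6.7 threshold to the delivered plan, which the protocol does not do. No probability in section 13.4 is wrong. The same section says that "a sample size 30 is assessed pragmatically and not based on hypothesis testing", so no formal error rate is breached. What is affected is the meaning of the rate on which the advance criterion rests.

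**What to change.** **Denominator and replacement (sections 13.2 and 12.2).** Define the feasibility denominator as all enrolled patients. State that a patient who leaves because single-fraction coverage was inadequate counts as not feasible, and that replacement does not remove that patient from the rate.

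**Second rate (section 13.2).** Prespecify a further feasibility rate in which a lesion is not a success if its delivered plan, predicted or adapted, shows the coverage loss described in section 6.7. Report it beside the primary rate. Say openly that this extends a threshold written for the original plan to the delivered plan, for analysis only. Whether the 80% criterion should rest on this stricter rate is for the sponsor to decide, and the choice should be stated before the data are seen.

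**Cost.** Predicted doses and adapted plans are already saved under sections 6.8 and 6.9. Coverage is not among the events listed for the time log, however, so sites would have to extract it lesion by lesion, for up to 10 lesions per patient. The reported feasibility figure may be lower. No dose, constraint or planning rule changes, and the text should say that the second rate gives no reason to depart from the priority of organ limits over coverage.
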